### 4.3 Pragmatic Features

Pragmatic trials combine the strength of randomized treatment assignment with design elements intended to maximize applicability of findings to diverse patient populations and clinical practice settings. With the goal of maximizing pragmatism, we applied the PRECIS-2 tool for trial design to assess the consistency of our design choices with our overall goals. We adhere to a highly pragmatic approach to eligibility, setting, care delivery models, flexibility of intervention delivery, and flexibility of intervention adherence. Our primary outcome, improvement in pain interference, is highly pragmatic because it is relevant to patients with chronic pain. Our care delivery models for the two active intervention arms are flexible. We will allow providers to conduct the active intervention visits in-person, through video platforms, or via telephone. To securely conduct video telehealth visits, providers are permitted VA Video Connect (VVC), Doximity, and/or Cisco WebEx. To securely conduct visits via telephone, providers may use: on-campus VA telephones, VA-issued cellular devices, soft lines, VANTS lines, and/or Doximity. These options for delivering the interventions are highly pragmatic and will enhance protocol adherence, especially in light of the COVID-19 pandemic and VHA's mandate to convert all elective healthcare to telehealth. We anticipate that veteran participants will be hesitant and/or unable to attend study visits in-person not only during the COVID-19 pandemic, but for an extended period thereafter. The variety of telehealth options offered for the active intervention arms are identical to the telehealth options that veterans are currently offered as part of usual primary care. Study clinicians will be trained in optimal use of all platforms offered at their respective sites and the use of any and all chosen platforms will be piloted by the clinical teams prior to use with enrolled participants.

The least pragmatic elements of our design are follow-up intensity and recruitment. Given the importance of patient-reported outcomes in pain research, we will have frequent follow-up contacts and telephone assessments by masked study staff members to reduce ascertainment bias, minimize missing outcome data, and reduce participant attrition. We will test the reliability of point of care and VA administrative data in comparison to patient-reported outcomes as another potential source of data that is more pragmatic. For recruitment, we are using a well-established centralized approach to achieve and retain the target sample size, while oversampling women (who are under-represented in the veteran population). We are also encouraging providers to refer patients to our study. Centralized and local recruitment efforts will attempt to address potential barriers to recruitment of patients with chronic pain, particularly those receiving opioids. One aspect that will make our recruitment more pragmatic in light of COVID-19 is to place participants on a secure call-back list if they are unable to participate due to COVID-19-related barriers at the time of recruitment but are interested in participating at a later date, not to exceed one year prior to study end.

The COVID-19 pandemic requires even greater pragmatism with respect to intervention delivery. Telehealth resources reflect an alternative way of delivering care when in-person care delivery may not be feasible or available, such as with the COVID-19 pandemic. Some participants may be less willing or able to use telehealth than others and thus with shelter-in-place orders or phased recovery plans, COVID-19 may impact subjects' ability to remain engaged in the study interventions and provide outcomes data. On the other hand, with more and more veterans learning to use telehealth and prohibitions on travel and relocation, more veterans may complete the study interventions and the follow-up assessments, providing outcomes data. Thus, given the unknown impact of COVID-19 pandemic on participants and study outcomes, we will need to plan for the possibility that a per-protocol analysis may be needed in addition to the planned intention-to-treat analysis (ITT). As opposed to the ITT analysis which includes all participants who were enrolled and randomized to one of the three study interventions, the per-protocol analysis includes only subjects who completed the protocol of the originally allocated treatment. This per-protocol effect is the maximum potential benefit of the active treatments and is estimated without being affected by incomplete adherence; therefore, the per protocol analysis may be of more interest for patients who consider whether to use the intervention. If using per-protocol analysis the effect size of a COVID-19 period is attenuated compared with that of a non-COVID period, we can infer that COVID-19 may have mitigated the effect of the intervention for a variety of reasons; e.g., telehealth vs. in-person intervention delivery; lack of available pain resources in VA or the community etc. On the other hand, if it is feasible to conduct both ITT and per-protocol analyses, and if the results agree, we can conclude that COVID-19 had limited influence on the treatment effects. In summary, we expect more pragmatic features in the "organization" and "primary analysis" domains of the PRECIS-2 Tool due to the impact of COVID-19.

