System-level variables: sites' degree of openness (fully closed/partially open/fully open (categorical), mode of treatment delivery (in-person, tele-health, phone, categorical), availability of non-pharmacologic pain management services (Yes/Partially yes/No, categorical); Individual-level variables: COVID infection status (categorical: yes, no, unknown), self-reported socio-economic outcomes such as lack of access to transportation, food, prescription refills, and community resources (categorical), health outcomes such as mental health and pain (categorical), number of missed intervention sessions. (numerical).

For the issues of fluctuations in mode of treatment delivery and temporal variations, our strategies are to: (1) adjust for time-dependent variables that reflect changes in the implementation of treatments, and (2) perform an exploratory analysis stratified by time periods sites, and site characteristics such as degree of openness. The exploratory analysis has an inherent limitation of inadequate power, because the analytical sample will be partitioned by time periods and sites.

We will also consider a per-protocol analysis to supplement the ITT analysis. This analysis includes only patients who minimally or completely adhered to treatment assignment indicated by the protocol, but will exclude the protocol violators who did not meet the following minimal threshold criteria: if randomized to the WHT arm, participants attended at least 6/8 coaching sessions, the WHT initial visit, and at least 2 of 3 follow-up WHT visits; if randomized to the PC-GE arm, participants attended the orientation and at least 4 of 5 core modules. In addition, participants will be excluded from the per-protocol analysis if they received prohibited concomitant interventions or if they missed all outcome measurements. We will follow recommendations by Hernan and Robins and adjust for both pre-randomization (baseline) and post-randomization prognostic factors. We will examine if the post-randomization prognostic factors are affected by prior treatment. If so, we will use the inverse-probability weighting method. This entails estimating a sequential propensity score based on post-randomization time-dependent factors and reweighting subjects using the propensity score estimated earlier. This method helps us minimize post-randomization confounding and selection bias.

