7.4 Exploratory Analyses/ Per Protocol Analyses

Responder analysis (exploratory analysis). Response will be defined as at least a 30% improvement in BPI interference score from baseline. Reduction in pain/interference of this size has been found to be clinically meaningful and IMMPACT recommended that the percentage of participants with this reduction be reported in chronic pain clinical trials.¹⁶ In addition, they recommended the percentages of patients with at least 50% improvement (substantial improvement) also be reported. We will also report the number who achieved a reduction in pain interference of at least 1 point (minimal clinically important difference for BPI interference).

With the COVID-19 pandemic, treatment implementation may have varied during the study period, and there may have been incomplete adherence to the interventions and outcome assessments. We collected additional time-dependent data to attempt to capture these fluctuations (variables such as mode of treatment delivery, availability of pain management services, and COVID infection status). Our strategies are to: (1) adjust for time-dependent variables that reflect changes in the implementation of treatments, and (2) perform analyses using interactions to see whether the treatment effect differs by time periods, sites, and site characteristics such as degree of availability of pain management services. Inherently these will have limited power, and no further adjustments will be made for multiple testing given the exploratory nature of these analyses.

Additional analyses will consider a per protocol population and repeat the primary analysis in this population. In the per protocol population, we will include any subject who minimally or completely adhered to treatment assignment indicated by the protocol, but will exclude the protocol violators who did not meet the following minimal threshold criteria: if randomized to the WHT arm, participants attended at least 6/8 coaching sessions, the WHT initial visit, and at least 2 of 3 follow-up WHT visits; if randomized to the PC-GE arm, participants attended the orientation and at least 4 of 5 core modules. In addition, participants will be excluded from the per-protocol analysis if they received prohibited concomitant interventions or if they missed all outcome measurements.

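### Protocol 4.3 lets a smaller per-protocol effect in an undefined COVID period support the inference that COVID-19 may have weakened the interventions, with no interval, margin or test

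*Protocol*

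**What the plan says.** Protocol 4.3 (Pragmatic Features) plans for a per-protocol analysis alongside ITT because of the pandemic. It then states that if the per-protocol "effect size of a COVID-19 period is attenuated compared with that of a non-COVID period, we can infer" that the pandemic may have reduced the intervention's effect. The reasons it gives as examples are delivery by telehealth rather than in person and a shortage of pain services.

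On the population, 4.3 says that "the per-protocol analysis includes only subjects who completed the protocol of the originally allocated treatment" and that the per-protocol effect "is estimated without being affected by incomplete adherence". Protocol 8.3 and 8.6 and SAP 7.4 set the attendance minimum: for WHT, 6 of 8 coaching sessions, the initial visit and 2 of 3 follow-up visits; for PC-GE, the orientation and 4 of 5 core modules. Usual Primary Care has no attendance minimum.

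On adherence, 4.3 looks both ways: "COVID-19 may impact subjects' ability to remain engaged in the study interventions and provide outcomes data", but also "more veterans may complete the study interventions and the follow-up assessments".

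Two other places deal with period differences. Protocol 8.6 will "perform an exploratory analysis stratified by time periods sites, and site characteristics such as degree of openness" and concedes that power is inadequate. SAP 7.4 will "perform analyses using interactions to see whether the treatment effect differs by time periods, sites, and site characteristics", and calls this exploratory with limited power. The SAP does not repeat the 4.3 inference, and its per-protocol analysis repeats the primary analysis without a comparison of periods.

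**The concern.** The 4.3 sentence turns a comparison of two estimates into a statement about cause, but gives no criterion for when one estimate counts as attenuated. The boundary between the periods is also open. The pandemic dates in Protocol 15 (Aim 3) belong to the retrospective national cohort and are not carried into 4.3, 8.6 or SAP 7.4. With 12 months of follow-up, one participant can fall in both periods, so the place of the cut matters.

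The population adds a second difficulty. If the pandemic weakened an intervention by keeping people from sessions, most of that loss is removed once the comparison is restricted to those who met the attendance minimum. Because attendance is determined after randomisation, the between-period contrast in that subset is not protected by randomisation either.

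At stake is the interpretation of the trial. A weak result in one period could be linked to the pandemic on a difference that chance alone produces often.

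**Working it through.** Protocol 4.3 states no figure of its own, so there is none to reproduce. The steps below show what the condition does when read literally.

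**Inputs from Protocol 8.2 and SAP section 4 (Sample Size).** Variance 5.90, so SD = √5.90 = 2.43 points; correlation 0.66; 341, 341 and 83 randomised; 20% attrition, giving 273 per active arm and 66 in UPC (0.8 × 83); effect size 0.15 for WHT vs PC-GE and 0.30 for each active arm vs UPC.

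**Assumptions not in the documents.** 40–100% of each active arm meets the per-protocol minimum; all UPC completers are kept; 30–70% of participants fall in the COVID period; the baseline-adjusted residual SD is 2.43 × √(1 − 0.66²) = 1.825. The effect size is read either as a standardised difference (0.15; 0.30) or as Cohen's f, which doubles it (0.30; 0.60). Clustering is ignored, so the standard errors are if anything optimistic.

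**Step 1: no COVID effect.** Let D be the COVID-period benefit minus the non-COVID-period benefit, both estimated. If the true effects are equal and selection does not differ by period, D is centred on zero and P(D < 0) = 0.50, whatever its standard error. Simulation over the assumed range gave 0.498–0.501. If selection does differ by period, the figure can move either way.

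**Step 2: precision.** For WHT vs PC-GE with 60% retention and an even split, the number per arm and period is 341 × 0.6 / 2 = 102.3. Then SE(D) = 1.825 × √(4/102.3) = 0.36 points. The whole assumed effect is 0.15 × 2.43 = 0.36 points. After 20% attrition the number is 273 × 0.6 / 2 = 81.9 and SE(D) = 0.40.

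**Step 3: the effect is truly halved.** P(D < 0) = Φ(half the effect / SE). With the pre-attrition figures, Φ(0.182/0.361) = 0.69. With the post-attrition figures, 60% retention and an even split:

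| Comparison, standardised difference | SE(D) | Smaller estimate, no COVID effect | Smaller estimate, effect halved | Power of interaction for halving* |
|---|---|---|---|---|
| WHT vs PC-GE, 0.15 | 0.40 | 0.50 | 0.67 | 0.07 |
| WHT vs PC-GE, 0.30 | 0.40 | 0.50 | 0.82 | 0.15 |
| Active vs UPC, 0.30 | 0.53 | 0.50 | 0.75 | 0.10 |
| Active vs UPC, 0.60 | 0.53 | 0.50 | 0.91 | 0.28 |

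*Two-sided 0.05, counting rejections in the direction of attenuation.

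Over the full range of assumptions, the third probability runs from 0.63 to 0.93. The ratio to 0.50 is 0.63/0.50 = 1.3 up to 0.93/0.50 = 1.9.

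**Step 4: what the planned interaction offers.** A two-sided 0.05 test would cut the false-signal rate from 50% to 5% per comparison (2.5% in the direction of attenuation). Its power for a true halving is about 5–31% over the whole range, and 8–31% at full retention, the case closest to an ITT analysis, if the same effect sizes hold there.

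**The case against.** The strongest reply is that 4.3 is a narrative section and its sentence is hedged: it infers a possibility, not a finding. Protocol 8.6 refers the reader to the Data Analysis Plan for the full statistical protocol. SAP 7.4 introduces its period interactions as a strategy for the pandemic, and both documents warn of low power. All of this stands, and it limits the weight of the point. What it does not do is connect the two: neither document says that the interaction, or its interval, decides when the 4.3 inference may be drawn.

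Several stronger readings are tempting and should be set aside.

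- *The protocol will conclude that COVID-19 weakened the interventions whenever the estimate is smaller.* It says only that this may have happened, and it leaves attenuated undefined. The 0.50 belongs to the literal reading. If the word meant at or below half of a positive non-COVID estimate, chance alone would meet it in about 3–33% of trials under the same assumptions.
- *The per-protocol set excludes the main pathway.* The documents rank no pathway. Section 4.3 allows that adherence could rise or fall, the telehealth and resource pathways it lists can act among adherers, and the attendance minimum tolerates some missed sessions. Protocol 8.6 and SAP 7.4 also plan adjustment or weighting for post-randomisation factors.
- *Some comparison will nearly always look attenuated.* At least one of the three does so in about 80% of simulated trials with no COVID effect, but the plan states no any-of-three rule.
- *A null result will be excused, or the later protocol overrides the SAP.* No text says so. The log for protocol version 2.3 lists no statistical change, so its later date shows no choice of 4.3 over the SAP.

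**Conclusion.** The point holds as a gap in the criterion for a hedged, secondary inference. Read literally, the condition in 4.3 is met half the time per comparison when COVID had no effect. That figure needs no assumption about sample size or period split, but it does require that per-protocol selection be the same in both periods. Under a true halving the condition is met 63–93% of the time; this range depends on the assumed retention, the assumed split and the two readings of the effect size. A signal only 1.3 to 1.9 times as likely under halving as under no effect is weak evidence, and it is read in a post-randomisation subset that largely hides one possible pathway. The primary ITT comparisons and their alpha levels are untouched. Severity is minor to moderate.

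**What to change.** In Protocol 4.3, replace the between-period inference with wording such as: *Any statement that COVID-19 modified the treatment effect will rest on the treatment-by-period interaction at 12 months described in SAP 7.4, estimated in the ITT population, reported with its confidence interval and labelled exploratory. A smaller point estimate in one period will not by itself be read as evidence of mitigation.*

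Also:

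- Define the COVID and non-COVID periods in SAP 7.4 before unblinding. Date of randomisation is one option; because delivery and follow-up run for 12 months, the choice should be justified.
- Align the stratified-by-period wording in Protocol 8.6 with the SAP interaction analysis.
- Keep per-protocol estimates by period as descriptive.

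The cost is a few sentences in two documents, with no new data and no new type of model. The SAP allows modification up to final data lock and before unblinding. The downside is that the interval will be wide, with power of about 5–31% for a true halving, so the trial will usually have to report the COVID question as unresolved. An ITT contrast also will not separate delivery mode from adherence, which is a reason to keep the descriptive per-protocol estimates beside it.

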## **5.0 Selection, Recruitment, and Enrollment of Participants**

### **5.1 Inclusion Criteria**

Participants must meet the following inclusion criteria to be enrolled in the study:

- Assigned to a VA PCP;

- Report pain present every day or nearly every day for  $\geq 6$  months using a phone eligibility screener; and
- PEG score of  $\geq 4$  (including at baseline assessment)

## 5.2 Exclusion Criteria

Candidates with any of the exclusion criteria at baseline will be excluded from study participation:

- Moderate or severe cognitive impairment as determined by a failed 6-item, validated cognitive screener on initial phone screening (see Appendix 1.0: Phone Eligibility Script/Screener);
- Active suicidality as determined by medical record review, standardized assessment (PHQ-9) and/or is unable to attend study visits because of an unstable or severe psychiatric or medical condition or is receiving palliative or hospice care; or
- Current involvement in any similar longitudinal interdisciplinary pain clinical service including local integrated/integrative pain management programs
- Any other factors that would interfere with study participation including inability to communicate by telephone; being a non-English speaker; plans to relocate within 12 months and concurrent participation in another pain-related study.

## 5.3 Recruitment

### Recruitment of Clinician Participants:

Local site investigators will identify volunteer clinician participants by discussing the study with local clinical colleagues, pain champions, and primary care teams. Local site investigators will share contact information with the San Francisco research staff, who will provide study information to potential clinician participants and invite them to participate. Written informed consent for participation will be obtained by the local site investigator or study coordinator at the local site level prior to the local site trial launch or, for clinicians who join after the trial launch, prior to their participation in the intervention teams. If a clinician prefers to become a member of the study team (study collaborator) instead of a participant, appropriate training and qualifications will be required.

### Sample Size

We plan to enroll up to 20 clinician participants at each site (including replacements over the course of the active intervention period), which we expect will be approximately evenly distributed across the 6 enrollment sites.

### Recruitment of Study Participants:

The total sample size for the population based on our main study aim/hypothesis is

N=765. This breaks down to N=341 in each of the active interventions (WHT and PC-GE) and N=83 in the Usual Primary Care arm (Control). In other words, we hypothesize that the effect size differences will be smaller between the two active interventions than for each of the active interventions compared to Usual Primary Care. Therefore, we will require the larger sample size to detect differences between the two active interventions than each compared to Usual Primary Care. At each of the initial five enrollment sites, we will need to enroll, on average, 69 patients each in the WHT and PC-GE arms and 17 patients in the Usual Primary Care arm over the enrollment period. We will be adding a sixth enrollment site to help achieve our target sample. While this is an average projection, we expect that enrollment rates will differ across sites and, consistent with the pragmatic trial design, we will allow sites to go over and under projected averages. Based on prior similar studies, given the pragmatic eligibility criteria, we anticipate that at a minimum, 70% screened will be eligible to participate and of those eligible, roughly 20% will enroll. If we require approximately 765 patients for the trial to test the primary study hypothesis, anticipating a 20% drop-out rate, we would need to screen 5,464 to identify roughly 3,825 potentially eligible patients.

**Table 1. Plan for recruitment of an adequate sample**

Total number of patients expected to be screened	~ 5,464
Of those screened, total number expected to be eligible:	~ 3,825
Target sample size:	~ 765

Compared to the general U.S. population, women are underrepresented in veteran samples. Thus, to achieve better representation of women in the pragmatic trial, we will oversample women by inviting *all* preliminarily eligible women and only a proportion of preliminarily eligible men. If estimated enrollment rates are accurate, we would then enroll women at approximately twice the rate of their prevalence in the veteran population. We will monitor enrollment of ethnic minority participants and if lower than that represented in the veteran population, we will prioritize recruitment of ethnic minorities. Historically, we have found it challenging to recruit veterans prescribed opioids for chronic pain into research studies of alternative management interventions. We will thus also over-sample veterans prescribed opioids.

